10.6 Safety Analyses

10.6.1 Adverse Events

The Medical Dictionary for Regulatory Activities (MedDRA) version 15.0 or later will be used to code all adverse events to a system organ class and a preferred term. All adverse event tables will be summarized by the randomized treatment group.

Treatment-emergent adverse events are events with an onset after the administration of the first dose of IP.

The subject incidence of adverse events will be summarized for all treatment-emergent, serious, treatment-related, serious treatment-related, those leading to withdrawal of investigational product, fatal, and special events of interest (EOI). Subject incidence of EOI will also be summarized according to their categories.

Subject incidence of all treatment-emergent, serious, treatment-related, serious treatment-related, those leading to withdrawal of investigational product, and fatal adverse events will be tabulated by system organ class and preferred term in descending order of frequency.

Subject incidence of all treatment-emergent adverse events will be tabulated by system organ class, high level group term, and preferred term. Summaries of treatment-emergent, serious, treatment-related, and serious treatment-related adverse events occurring in at least 5% of the subjects by preferred term in any treatment arm will be provided in descending order of frequency of the Hb-based titration group. Risk difference and its 95% CI of each preferred term of AE and SAE will be tabulated in descending order of the risk difference.

Subgroup analyses for stratification factors, age group, race, gender, baseline Hb, baseline eGFR and diabetes at baseline will be presented by system organ class and preferred term in descending order of frequency.

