7.2.8 Adverse Events

The incidence of adverse events will be collected for each subject at all study visits. A serious adverse event that occurs in a subject after signing the informed consent but prior to randomization will be recorded on the screening serious adverse event eCRF. All adverse events that occur after randomization through 4 weeks after the last dose of investigational product will be recorded on the adverse event eCRF and on the serious adverse event eCRF if they are serious. See [Section 9](#) for additional information.

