9.1.2 Reporting Procedures for Adverse Events

The investigator is responsible for ensuring that all adverse events observed by the investigator or reported by the subject that occur after randomization through 4 weeks after the last dose of investigational product are reported using the applicable eCRF (eg, Adverse Event Summary eCRF).

The investigator must assign the following adverse event attributes:

- Adverse event diagnosis or syndrome(s), if known (if not known, signs or symptoms),
- Dates of onset and resolution,
- Severity [and/or toxicity per protocol],
- Assessment of relatedness to darbepoetin alfa, and
- Action taken

The adverse event toxicity grading scale used will be the Amgen adverse event standard grading score. The toxicity grading scale used in this study is described in [Appendix B](#).

The investigator must assess whether the adverse event is possibly related to darbepoetin alfa. This relationship is indicated by a "yes" or "no" response to the question: Is there a reasonable possibility that the event may have been caused by darbepoetin alfa?

The investigator must assess whether the adverse event is possibly related to a device. This relationship is indicated by a "yes" or "no" response to the question: Is there a reasonable possibility that the event may have been caused by a device?

The investigator must assess whether the serious adverse event is possibly related to any study-mandated screening procedure. This relationship is indicated by a “yes” or “no” response to the question: “Is there a reasonable possibility that the event may be related to screening procedures?”

The investigator must assess whether the adverse event is possibly related to any study-mandated activity or procedure. This relationship is indicated by a “yes” or “no” response to the question: “Is there a reasonable possibility that the event may have been caused by a study activity/procedure?”

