9.2.2 Reporting Procedures for Serious Adverse Events

The investigator is responsible for ensuring that all serious adverse events observed by the investigator or reported by the subject that occur after signing of the informed consent through 4 weeks after the last dose of investigational product are recorded in the subject’s medical record and are submitted to Amgen. Any serious adverse events with a fatal outcome (regardless of possible relationship to investigational product) occurring through the end of the subject’s participation on the study are to be reported to Amgen. This would include subjects who have been removed from investigational product and continued on-study.

After the protocol-required reporting period defined above, the investigator does not need to actively monitor subjects for serious adverse events. However, if the investigator becomes aware of a serious adverse event after this protocol-required reporting period, the investigator will report the event to Amgen within 24 hours following the investigator’s knowledge of the event. Serious adverse events reported outside of the protocol-required reporting period will be captured within the safety database as clinical trial cases for the purposes of expedited reporting.

The serious adverse event must be submitted to Amgen within 24 hours following the investigator’s knowledge of the event via the applicable eCRF. If the electronic data capture (EDC) system is unavailable to the site staff to report the Serious Adverse Event, the information is to be reported to Amgen via an electronic Serious Adverse Event (eSAE) Contingency Report Form within 24 hours of the investigator’s knowledge of the event. See [Appendix C](#) for a sample of the Serious Adverse Event Worksheet/eSAE Contingency Report Form. When the first notification of a Serious Adverse Event is reported to Amgen via the eSAE Contingency Report Form, the data must be entered into the EDC system when the system is again available.

The investigator must assess whether the serious adverse event is possibly related to any study-mandated activity or procedure. This relationship is indicated by a “yes” or “no” response to the question: “Is there a reasonable possibility that the event may have been caused by a study activity/procedure”?

The investigator is expected to follow reported serious adverse events until stabilization or reversibility.

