Defined as the number and percentage of subjects with a reported event(s). For subjects with multiple reports of the same event during the study, the subject will be counted only once. If a pre-existing condition worsens on or after the first dose of investigational product administered, the event will be counted as if it occurred on the day it worsened. For adverse event tabulations involving relationship to investigational product, the subject is counted in the tabulations if at least 1 occurrence of the event is

related. For adverse event tabulations involving severity, the highest severity of the particular adverse event will be used for each subject.

Hemoglobin

For all Hb-related endpoints, the Hb measured using the point of care device will be used. For Hb measured by the central laboratory, they will only be summarized descriptively by treatment group at each scheduled visit.

Achieved Hb Concentration while Receiving Investigational Product

For each subject, the achieved Hb concentration while receiving IP will be derived using the area under the curve (AUC) method with all Hb measured during the period starting from Week 13 (Study Day 85) to the last dose date will be included in the calculation. The 12 week interval is indicated in the USPI as escalation period.

Post-baseline Hb Concentration Subgroup

Post-baseline Hb concentration subgroup is defined as < 8.0, ≥ 8.0 and < 9.0, ≥ 9.0 and < 9.5, ≥ 9.5 and < 10.0, ≥ 10.0 and ≤ 10.5, > 10.5 and ≤ 11.0, > 11.0 and ≤ 12.0, > 12.0 and ≤ 13.0, > 13.0 g/dL

Hb Rate of Change (ROC)

Only Hb measured on and after Study Day 1 and while the subject is receiving the investigational product will be included in the calculation.

ROC (g/dL per 4 weeks) is calculated using the following equation:

$$\text{ROC (g/dL/4weeks)} = [(\text{Hb at visit X} - \text{Hb at Visit Y}) / (\text{Date of Visit X} - \text{Date of Visit Y})] * 28, \text{ where X and Y are consecutive post-baseline visits.}$$

Time to Reach Hb ≥ 10.0 g/dL

Time from the Study Day 1 to the date the Hb measurement reached ≥ 10.0 g/dL for the first time. Subjects who never reach Hb ≥ 10.0 g/dL will be censored on the last date of IP.

Proportion of Hb measurements ≥ 10.0 g/dL

Proportion of Hb measurements ≥ 10.0 g/dL = the number of Hb measurements ≥ 10.0 g/dL / Total number of Hb measurements. Only Hb measured on or after Study Day 1 and while the subject is receiving the investigational product will be included in the calculation.

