10.5.1 Analyses of Primary Efficacy Endpoint(s)

The primary analysis of the primary endpoint will be conducted using the full analysis set. The evaluation period will begin from the date of randomization, and subjects will be censored at the last dose of investigational product plus 3 months or end of study, whichever is earlier (on-treatment approach). For the primary endpoint, the proportion of subjects in each treatment group receiving at least 1 RBC transfusion during the evaluation period will be presented with 2-sided 95% CIs. The difference in proportions between treatment groups will be described with 2-sided 95% CIs. Confidence intervals

will be derived using normal approximation. The relative risk ratio and its 95% CI will be described using the Cochran-Mantel-Haenszel statistic controlling for the stratification factors.

The primary analysis will be repeated by subgroups of stratification factors used at randomization, and also by subgroups of age, gender, race, baseline Hb concentrations, baseline eGFR and diabetes at baseline.

Sensitivity analyses of the primary endpoint will be repeated using:

- All randomized subjects with the evaluation period beginning at the date of randomization and subjects will be censored at the end of study date (on-study approach).
- Completer analysis set with the evaluation period between the date of randomization and the end of study date

Sensitivity analyses will be performed to assess the impact of potential differential follow up on the primary endpoint. Exposure-adjusted subject incidence of receiving at least 1 RBC transfusion will be calculated with 95% CI using Chi-square approximation to the Poisson distribution for both on-treatment and on-study approaches.

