10.5.3 Analyses of Exploratory Endpoints

The following exploratory endpoints will be summarized by each treatment group using the full analysis set:

- Darbepoetin alfa dose and weight-adjusted dose received at each study visit
- Hb concentration and its subgroup at each study visit
- Hb concentration change from baseline at each study visit
- Time to first Hb concentration ≥ 10.0 g/dL
- Proportion of Hb measurements ≥ 10.0 g/dL
- Hb rate of change in a 4 week interval at each study visit
- Hb variability at each study visit
- Anti-HLA antibodies as measured using panel reacted antibodies (PRA) over time based on both on-treatment and on-study approaches

Anti-HLA antibodies over time will be summarized by the transfusion subgroup (on-treatment approach) and by randomized treatment group using the full analysis set. The summary will be repeated by the transfusion subgroup (on-study approach) and by randomized treatment group using all randomized subjects.

Furthermore, the following Hb-related information will be evaluated and summarized by randomized treatment group using the full analysis set

- At least one Hb < 8.0 g/dL and the proportion of the Hb measurements < 8.0 g/dL
- At least one Hb < 9.0 g/dL and the proportion of the Hb measurements < 9.0 g/dL
- At least one Hb > 11.0 g/dL and the proportion of the Hb measurements > 11.0 g/dL
- At least one Hb > 12.0 g/dL and the proportion of the Hb measurements > 12.0 g/dL
- At least one Hb > 13.0 g/dL and the proportion of the Hb measurements > 13.0 g/dL

Number of days hospitalized will be summarized by treatment group using the on-treatment approach and the full analysis set. As a sensitivity analysis, the number of days hospitalized will also be summarized by treatment group using the on-study approach and all randomized subjects.

Initial Hb response at Week 5 will be summarized by treatment group using initial Hb response analysis set. The following will be summarized by initial Hb-response subgroup and treatment group using the initial Hb response analysis set:

- Hb concentration at each study visit and the achieved Hb
- Darbepoetin alfa dose at each study visit and the cumulative dose

Subjects received ≥ 1 RBC transfusion and time to first RBC transfusion will be descriptively summarized by the initial Hb response subgroup using on-treatment approach.

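### Adverse-event risk differences are crude although collection ends 4 weeks after the last dose, so they may be biased if stopping of treatment differs by arm; exposure-adjusted rates should be added

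*SAP*

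**What the plan says.** SAP 6.3 defines adverse-event subject incidence as a count and percentage of subjects, each counted once per event, with no time denominator. On that measure SAP 10.6.1 states: "Risk difference and its 95% CI of each preferred term of AE and SAE will be tabulated in descending order of the risk difference". The adverse-event tables listed in SAP 12.1 contain no exposure-adjusted, time-to-event or on-study version.

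The observation window comes from the protocol. Protocol 7.2.8 says: "All adverse events that occur after randomization through 4 weeks after the last dose of investigational product will be recorded on the adverse event eCRF". Protocol 9.2.2 sets the same end for serious events, namely those "that occur after signing of the informed consent through 4 weeks after the last dose of investigational product". The exception, also in 9.2.2, is serious events with a fatal outcome, which are reported to the end of the subject's participation.

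Elsewhere the plan deals with unequal follow-up. For transfusion, SAP 10.5.1 says: "Sensitivity analyses will be performed to assess the impact of potential differential follow up on the primary endpoint", and it plans exposure-adjusted incidence on both the on-treatment and on-study approaches. SAP 10.5.2 adjusts units transfused and cumulative dose for exposure. SAP 6.3 defines exposure to investigational product as last dose minus first dose plus 1, plus 28 days, which is close to the adverse-event collection window.

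For hospital days, SAP 10.5.3 says: "Number of days hospitalized will be summarized by treatment group using the on-treatment approach and the full analysis set". The next sentence adds an on-study summary in all randomized subjects. SAP 6.3 ends the on-treatment count at last dose plus 84 days or end of study, whichever is earlier.

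**The concern.** A subject whose last dose is at Week 21 (day 141) has adverse events collected to day 169, about 24 weeks. A completer dosed at Week 97 (day 673) is followed to day 701, about 100 weeks. A crude percentage treats the two as equally observed.

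This matters only if stopping differs between arms, and there is reason to expect that it might. Protocol 6.4.1.2 allows upward titration in one arm and holds the dose in the other, and Protocol 8.1 lists lack of efficacy as a reason to end investigational product. The SAP takes the possibility seriously enough to analyse transfusion or stopping for lack of efficacy by arm (10.5.1). Protocol 2.3 says that adverse events will help to determine the preferred regimen, so a shift in the same direction across many terms would bear on that judgement.

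**Working it through.** **Inputs from the documents.** 375 subjects per arm (Protocol 10.2: 300/(1 - 0.20) = 375); 100 weeks on study (Protocol 3.4.1); collection to last dose + 4 weeks. SAP 10.6.1 states no figure of its own to reproduce.

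**Assumptions, because the documents give no value.** Event risk over 100 weeks, R = 10%, 30% or 50%; constant hazard, equal in both arms; stopping unrelated to events. The share stopping early is 20% in arm A and 30%, 40% or 50% in arm B. The last dose of early stoppers is spread evenly over the 24 visits from Week 1 to Week 93, so they are observed for u = 4, 8, ..., 96 weeks.

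**Formulas.**
- Risk observed in early stoppers: r = 1 - (1/24) × Σ (1 - R)^(u/100).
- Crude risk in an arm with share d stopping early: d × r + (1 - d) × R.
- Spurious difference, B minus A: -(dB - dA) × (R - r).
- Sampling SE of a difference: √(2R(1 - R)/375).

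**Example, R = 30%, stopping 20% against 40%.** r = 15.93%. Arm A: 0.20 × 15.93 + 0.80 × 30 = 27.19%. Arm B: 0.40 × 15.93 + 0.60 × 30 = 24.37%. The difference is -2.8 points although the true hazards are equal.

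| R | r | 20% vs 30% | 20% vs 40% | 20% vs 50% | SE | 1.96 × SE |
|---|---|---|---|---|---|---|
| 10% | 5.09% | -0.5 | -1.0 | -1.5 | 2.19 | 4.3 |
| 30% | 15.93% | -1.4 | -2.8 | -4.2 | 3.35 | 6.6 |
| 50% | 27.98% | -2.2 | -4.4 | -6.6 | 3.65 | 7.2 |

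Columns 3 to 7 are percentage points. The bias exceeds one SE in three of the nine cells (R = 50% at 40% stopping; R = 30% and 50% at 50% stopping) and never reaches the 95% CI half-width.

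**Second model, to test the stopping pattern.** With exponential stopping and 0.05 to 0.50 events per year, the spurious difference is -0.5 to -2.8, -1.0 to -5.7 and -1.5 to -8.8 points for 30%, 40% and 50% stopping in arm B. It exceeds the CI half-width only in the extreme cell (50% stopping, 0.50 per year: 8.8 against 7.1). A true hazard ratio of 1.06 to 1.09, 1.14 to 1.19 or 1.24 to 1.32 respectively would give a crude difference of zero. The exposure-adjusted rates are equal in the two arms in every equal-hazard scenario, for example 0.200 against 0.200 per year.

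**Hospital days.** In the second model, with an assumed 6 days per year, on-treatment totals are 10.55 in arm A against 10.03, 9.47 and 8.88 in arm B, ratios of 0.95, 0.90 and 0.84. On-study totals with full follow-up are 6 × 701/365.25 = 11.5 in both arms.

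**The case against.** A reader might infer that the arm with more early stopping is bound to look safer. The documents do not support that. They give no stopping rate by arm, and the 20% in the sample-size section is an overall dropout allowance. Protocol 2.3 says that the fixed dose was chosen by simulation to give about the same mean hemoglobin, and dialysis or transplant ends treatment in either arm. With equal stopping the bias is zero. A large true excess also survives it: with a true hazard ratio of 1.5 at 0.20 events per year, the arm with more stopping still looks worse by 8.8, 6.6 and 4.2 points at 30%, 40% and 50% stopping. Stopping caused by adverse events can also reverse the direction. If events cluster early (hazard tripled in the first 12 weeks, an assumption), the 20% against 40% figures shrink to -0.8, -2.3 and -3.5 points. The larger figures need single terms with 100-week risks of 30% to 50%, which is high for one preferred term.

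A reader might also infer that the whole safety comparison is exposed. It is not. SAP 10.6.2 analyses adjudicated death, stroke, myocardial infarction, heart failure, thromboembolism and access thrombosis by Kaplan-Meier, on-treatment and on-study, and fatal serious events are reported to the end of participation. Nor are hospital days left uncorrected, since the on-study summary does not stop after the last dose and the endpoint is exploratory.

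Finally, SAP 10.2 and 10.6.6 show stopping and exposure by arm, so an imbalance would be visible, and no hypothesis is tested.

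All of this limits the point without removing it. Showing an imbalance does not adjust for it. The further sensitivity analyses allowed for in SAP 9.4 concern the primary endpoint. Hypertension, convulsions, hypersensitivity, malignancies and the general run of adverse and serious events have no analysis that allows for time at risk.

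**Conclusion.** The point holds in conditional form. If stopping differs by arm, the crude adverse-event and serious-event differences may be biased in favour of the arm with more early stopping. The size is about -0.5 to -2.2 points for 20% against 30% stopping, -1.0 to -4.4 for 20% against 40%, and -1.5 to -6.6 for 20% against 50%, over 100-week risks of 10% to 50%. This rests on equal constant hazards, stopping unrelated to events, and stopping shares that are assumed. For any one term the bias is mostly smaller than the sampling error, but it pushes many terms the same way. The main inconsistency is that the SAP adjusts transfusion for follow-up and already defines the exposure needed, yet does not use it for adverse events. For hospital days only a minor gap remains: neither total is divided by time, so death or withdrawal shortens both, and the on-treatment total also shortens when treatment stops.

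**What to change.** In SAP 10.6.1 and the table list in 12.1, add exposure-adjusted subject incidence beside the crude counts: subjects with the event divided by person-time to first event or to last dose + 28 days, based on the exposure defined in SAP 6.3, with rate difference and 95% CI. Do this for all treatment-emergent events, serious events, events of special interest, and preferred terms at or above 5%. Count only events with onset inside that window. This should be stated, because the SAP definition of treatment-emergent has no end date and fatal serious events are reported later. Keep those later events in the crude tables. The planned ordering by crude risk difference can stay; ordering by rate difference would be a matter of preference.

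In SAP 10.5.3, also give hospital days per patient-year, each total divided by follow-up in its own window: to last dose + 84 days or end of study, whichever is earlier, for on-treatment, and to end of study for on-study.

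The cost is extra columns in planned tables, with no new data. The downside is that a rate summarises well only when the hazard is roughly constant, which is why the crude counts stay alongside. This is a cheap improvement.

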10.6.2 Major Clinical Events

Time to adjudicated major clinical events (as specified in [Section 4.3](#)), will be summarized by each treatment group with Kaplan-Meier curves, Kaplan-Meier percentiles, the number of subjects censored, and the number of subjects with events, using both on-treatment approach with the full analysis set, and on-study approach with

all randomized subjects. Subgroup analyses for the initial Hb response subgroup will be presented using both on-treatment and on-study approaches and the initial Hb response analysis set.

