6.3 Other Study Related Definitions

Analytical Window Assignments

Analytical windows will be used to summarize protocol specified parameters according to the protocol schedule. This algorithm is provided in [Appendix A](#).

Analytical Window Assignments

Analytical windows will be used to summarize protocol specified parameters according to the protocol schedule.

Exposure to Investigational Product

For each subject who received at least one dose of IP, the number of days of IP exposure Period is calculated as [(Date of Last Dose of Investigational Product Received – first dose date + 1) + 28 days]. The exposure to IP in study month = exposure to IP / 28 days.

Study Exposure

For each randomized subject, study exposure is defined as time from the randomization date to the end of study date.

Evaluation Periods for Different Analysis Approaches

The evaluation period of the on-treatment approach begins from the date of randomization, and subjects will be censored at the last dose of investigational product plus 3 months or end of study, whichever is earlier.

The evaluation period of the on-study approach begins at the date of randomization and subjects will be censored at the end of study date.

Treatment Emergent Adverse Events

Treatment emergent adverse events are adverse events occurring on or after the first dose of IP.

Adverse Events of Special Interest

Adverse events falling into categories of special interest (EOI) will be reported according to the special interest category. The categories of interest for the study are:

- Hypertension
- Ischemic Heart Disease
- Cardiac Failure
- Cerebrovascular Disorders
- Dialysis Vascular Access Thrombosis
- Embolic and Thrombotic Events (including arterial thromboembolic events, venous thromboembolic events and vessel type unspecified and mixed arterial and venous)
- Convulsions
- Antibody-Mediated Pure Red Cell Aplasia (PRCA)
- Hypersensitivity
- Lack of Efficacy-Effect
- Malignancies

The definition of each EOI may be modified and a new EOI may be added based on findings from ongoing pharmacovigilance. Updates of the search strategy due to MedDRA upgrades or other reasons may not trigger a SAP amendment. However, the most recent EOIs per Amgen EOI search strategy will be used at the time of the analysis and these search terms will be included in an appendix of the study report.

Adverse Event Subject Incidence

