Hb variability

At any study visit, the Hb variability is the intra-subject Hb standard deviation over the prior 6 months. The Hb variability will be calculated at each scheduled visit from Week 25.

Initial Hb Response

Initial Hb response is defined as the change of Hb concentration from baseline at Week 5.

Initial Hb Response Subgroup

Initial Hb response subgroups are defined as the initial Hb response quartiles based on the initial Hb response analysis set subjects ([Section 7.3](#)) from both treatment groups.

Dose

The dose referred in this analysis plan is the darbepoetin alfa dose from the IP administration. The dose from a placebo injection equals zero darbepoetin alfa dose.

Weight-based Dose at Specific Study Visit

The weight-based dose at any time point = Dose in μg at specific study visit / subject's screening weight in kg.

Cumulative Dose at Specific Study Visit

The cumulative dose at specific study visit = sum of all darbepoetin alfa doses received from Study Day 1 through the specific study visit.

Average Cumulative Dose per 4 Week at Specific Study Visit

Average cumulative dose per 4 week at specific study visit is defined as the 4-week equivalent cumulative dose received at specific study visit.

Average Cumulative Weight-adjusted Dose per 4 Week at Specific Study Visit

Average cumulative weight-adjusted dose per 4 week at specific study visit = average cumulative dose per 4 week at specific study visit / the screening weight in kg.

Transfusion Subgroups

Subjects will be categorized into transfusion subgroups based on the number of transfusion events: No transfusion event, one transfusion event, more than 1 transfusion event.

Transfusion subgroup (on-treatment approach) will be defined using the number of transfusion events where the start date of the transfusion event falls within the evaluation period of the on-treatment approach.

Transfusion subgroup (on-study approach) will be defined using the number of transfusion events where the start date of the transfusion event falls within the evaluation period of the on-study approach.

Time to Event Derivation

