For time to event such as time to first transfusion, or time to first major clinical event (eg, major adverse cardiovascular events (MACE), all-cause mortality), time to event is derived from the randomization date to the date of specific event. Subjects that do not experience the event will be censored. For time to event analysis using the on-treatment approach, the censoring date is the last dose date + 3 months (84 days) or the end of study date, whichever is earlier. For time to event analysis using the on-study approach, the censoring date is the end of study date.

Context surrounding RBC Transfusion

Clinical context surrounding RBC transfusion will be collected for each RBC transfusion event, and will be reviewed by an independent Clinical Endpoint Committee (CEC). The clinical context includes the primary reason for the transfusion event, the transfusion setting (eg, dialysis center, intensive care unit, emergency department), Hb at the time of the first transfusion of the transfusion event, clinical events (eg, bleeding, surgery), symptoms and vital signs of concerns.

Total number of units of RBC transfused

The total number of units of RBC transfused using the on-treatment approach is the sum of RBC units transfused between the randomization date and the earlier date of the last dose date + 3 months (84 days) and the end of study date. The total number of units of RBC transfused using the on-study approach is the sum of RBC units transfused between the randomization date and the end of study date.

Number of Days Hospitalized

This is the total number of days of hospitalization between the randomization date and earlier of the date of last IP + 3 months (84 days) and the end of study date for the on-treatment approach; between the randomization date and the end of study date for the on-study approach. Duration of each hospitalization stay is calculated as day of discharge - day of admission + 1. Hospitalizations with identical admission and discharge days will be counted as a hospitalization with duration of 1 day.

Area under the Curve (AUC) Calculation

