7.3 Initial Hb Response Analysis Set

The initial Hb response analysis set will include all randomized subjects who receive at least 1 dose of investigational product, excluding those who ended investigational product prior to Week 5 or those who do not have Hb measurement at Week 5.

Subjects will be analyzed according to their randomized treatment assignment. Subjects

will be excluded if: they do not receive the first dose at Day 1, they receive RBC transfusion during the period from randomization to prior to Week 5, they end investigational product prior to Week 5, or they do not have a Hb measurement at Week 5.

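### Summaries by Week 5 Hb response count time from randomization, so non-fatal major clinical events before Week 5 are attributed to a response measured after them

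*SAP*

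**What the plan says.** SAP 6.3 defines the grouping variable: "Initial Hb response is defined as the change of Hb concentration from baseline at Week 5". The groups are quartiles pooled over both arms: "Initial Hb response subgroups are defined as the initial Hb response quartiles based on the initial Hb response analysis set subjects".

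SAP 7.3 restricts the set to subjects who took product on Day 1, were still on product at Week 5 and have a Week 5 Hb. It also removes subjects if "they receive RBC transfusion during the period from randomization to prior to Week 5". It does not mention earlier major clinical events.

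The clock is set once, in SAP 6.3, for all time-to-event variables: "time to event is derived from the randomization date to the date of specific event". The two evaluation periods agree: "The evaluation period of the on-treatment approach begins from the date of randomization", and "The evaluation period of the on-study approach begins at the date of randomization and subjects will be censored at the end of study date".

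Two families of output combine these definitions:

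- **Major clinical events** (SAP 10.6.2): "Subgroup analyses for the initial Hb response subgroup will be presented using both on-treatment and on-study approaches and the initial Hb response analysis set". The planned tables in SAP 12.1 repeat the main analysis for this set.
- **Transfusion** (SAP 10.5.3): the proportion transfused and "time to first RBC transfusion will be descriptively summarized by the initial Hb response subgroup using on-treatment approach". SAP 12.3 adds a figure of the latter.

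The readable text has no landmark, delayed entry or removal of earlier events. The code fragments in SAP Appendix B are blacked out, so nothing can be inferred from them. The definitions in SAP 6.3 are legible and apply generally.

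**The concern.** Subjects are classified by a value that does not exist until about four weeks after the clock starts. What happens in those weeks depends on the endpoint.

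A subject who has a stroke, MI, heart failure episode or thrombosis in weeks 1 to 4, stays on product, is not transfused and has a Week 5 Hb remains in the set. The event is then plotted under a response quartile measured after it. Protocol 2.1 itself notes that an intercurrent clinical event, such as bleeding, infection or inflammation, can worsen anemia. An early event could therefore lower the measured response and move the subject into a poorer quartile. Part of any excess of events among poor responders would then run from event to response.

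Transfusion and death cannot occur in the set before the Week 5 cut-off, so those curves begin with a flat stretch. The two composites mix the problems: early deaths are impossible, but early non-fatal components are counted.

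What is at stake is how prespecified Kaplan-Meier displays of cardiovascular safety by initial response are read.

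**Working it through.** **Plan figures used.** SAP 3.2 assumes 25% of subjects transfused and derives 300 per group. At 25%, the width of the 95% CI per arm is 2 × 1.96 × √(0.25 × 0.75 / 300) = 9.8%, and for the difference 2 × 1.96 × √(2 × 0.25 × 0.75 / 300) = 13.9%. Allowing for dropout, 300 / (1 − 0.20) = 375 per group, or 750 in total. These figures reproduce. The plan gives no figure for the response-subgroup analyses and no rate for major clinical events.

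**Length of the period before the response.** Follow-up is 100 weeks, or 700 days (Protocol 3.4.1). Week 5 is planned for Day 29 (SAP Appendix A), but SAP 7.3 does not tie its Week 5 cut-off to a date.

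| Reading of Week 5 | Days before it | Share of 700 days |
|---|---|---|
| Planned Day 29 | 28 | 4.0% |
| Visit window of ±5 days (Protocol 7.1.4.1) | 23 to 33 | 3.3% to 4.7% |
| Analytical window, Days 15 to 42 (SAP Appendix A) | 14 to 41 | 2.0% to 5.9% |

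**Non-fatal major clinical events.** Assume a proportion q of 750 subjects has such an event over 100 weeks at constant hazard. The expected number with it in the first 4 weeks is 750 × [1 − (1 − q)^(4/100)].

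| Assumed q | Subjects with event before Week 5 | Per quartile, if spread evenly | Share of subjects with events |
|---|---|---|---|
| 5% | 1.5 | 0.4 | 4.1% |
| 10% | 3.2 | 0.8 | 4.2% |
| 20% | 6.7 | 1.7 | 4.4% |
| 30% | 10.6 | 2.7 | 4.7% |
| 40% | 15.2 | 3.8 | 5.1% |

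These counts use all 750 subjects. The set is smaller, because some subjects with early events would also be transfused, stop product or miss the Week 5 Hb. Spread evenly, these events would hardly affect the contrast between quartiles; bias arises only so far as they cluster.

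**Transfusion.** At 25% over 100 weeks, the hazard is −ln(0.75)/100 = 0.002877 per week. In the first 4 weeks 1 − exp(−4 × 0.002877) = 1.1% of subjects, or 8.6 of 750, would be transfused and so dropped from the set. In the remaining set, with nominal Week 5 timing, the curve at Day 168 (24 weeks) reads 1 − exp(−20 × 0.002877) = 5.6%. A landmark curve 24 weeks after Week 5 reads 1 − exp(−24 × 0.002877) = 6.7%. At 48 weeks the pair is 11.9% and 12.9%. The two curves in each pair measure time from different origins, 28 days apart.

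**The case against.** **The transfusion and mortality curves are not wrong.** A reader might infer that the plan understates transfusion, showing 5.6% where 6.7% is right. That does not follow. SAP 7.3 openly conditions on being untransfused and on product to Week 5. Given that, 5.6% is the correct risk by Day 168 under the model, and 6.7% is the risk 168 days after Week 5, at about Day 196. The difference is a shift of the time axis, the same for every quartile and both arms. This objection stands in full.

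**The stated aim is narrower.** A reader might also infer that the trial sets out to learn whether poor response predicts cardiovascular events. Protocol 1.4 and 2.3 and SAP 2.4 state the aim only as dose and achieved Hb by initial response. Event summaries by response enter through SAP 10.5.3 and 10.6.2 as descriptive output, with no hazard ratio or prognostic model between quartiles. This also stands; the point rests on those planned outputs alone.

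**Early events may be rare.** Protocol 4.1 requires clinical stability. Protocol 4.2 excludes stroke or MI within 24 weeks of screening, hospitalization or clinically relevant bleeding within 8 weeks, and any of these during screening. The early hazard could be below the constant-hazard figure. It could also be above it; the documents do not settle this.

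**Endpoint-specific exclusions are more than one sentence of work.** This is fair, and the cost below allows for it.

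None of these objections answers the non-fatal events. SAP 7.3 removes early transfusions but has no corresponding rule for early major clinical events.

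**Conclusion.** The point holds for non-fatal major clinical events and for the composites that contain them. Events before Week 5 are counted under a response measured later, and this could bias the comparison between quartiles. Reverse causation is possible but not shown: a reader might infer that poor responders will display a spurious excess, but the documents establish neither its existence nor its direction.

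The size is small: about 1.5 to 15 subjects with such an event before Week 5. That rests on an assumed two-year proportion of 5% to 40%, a constant hazard, all 750 subjects and a nominal 28 days.

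For transfusion and death, the effect is an event-free start of nominally 28 days (23 to 33 or 14 to 41, depending on how Week 5 is read). By itself it does not bias the comparison between quartiles. The primary analysis, the sample size and the main between-arm summaries in SAP 10.6.2 are unaffected. This is a cheap improvement.

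**What to change.** Add a landmark rule to SAP 6.3, applying to every incidence or time-to-event summary by initial Hb response in SAP 10.5.3 and 10.6.2 and the matching tables and figures in SAP 12:

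- Start time at the date of the Week 5 Hb and count only later events. Keep the existing censoring dates.
- For each non-fatal endpoint, exclude subjects who already had that event after randomization and before the landmark. For a composite, exclude subjects who already had any component. Report the number excluded by quartile and arm.
- Keep all subjects of the set in the all-cause and cardiovascular mortality summaries, so that a death after an early non-fatal event is still shown there even though the subject leaves the composite.
- Use the same date for the Week 5 cut-off in SAP 7.3.

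No new data are needed. About 4% of non-fatal events are lost from these subgroup summaries, and essentially none for transfusion or death, because the set already excludes them. The real cost is programming the endpoint-specific exclusions.
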